#### 8.1.2. *Discontinuation of Inadvertently Enrolled Subjects*

If the sponsor or investigator identify a patient who did not meet enrollment criteria and was inadvertently enrolled, a discussion must occur between the sponsor CRP and the investigator to determine if the patient may continue in the study. If both agree it is medically appropriate to continue, the investigator must obtain documented approval from the sponsor CRP to allow the inadvertently enrolled patient to continue in the study with or without treatment with investigational product.

## 8.2. Discontinuation from the Study

Some possible reasons that may lead to permanent discontinuation include:

- enrollment in any other clinical trial involving an investigational product or enrollment in any other type of medical research judged not to be scientifically or medically compatible with this study. **Note:** Enrollment in the separate long-term extension study shall be considered compatible with Study AMAF, provided that the subject is not permanently discontinued from treatment or from the study, and provided that the subject is deemed eligible for enrollment in the separate long-term extension study.
- participation in the study needs to be stopped for medical, safety, regulatory, or other reasons consistent with applicable laws, regulations, and good clinical practice (GCP)
- investigator decision
  - the investigator decides that the subject should be discontinued from the study
  - if the subject, for any reason, requires treatment with another therapeutic agent that has been demonstrated to be effective for treatment of the study indication, discontinuation from the study occurs prior to introduction of the new agent
- subject decision
  - the subject requests to be withdrawn from the study
- AE
  - If the investigator decides that the subject should be withdrawn because of an AE/SAE or a clinically significant laboratory value, the investigational product is to be discontinued and appropriate measures are to be taken. Lilly or its designee is to be alerted immediately. Refer to Safety Evaluations, Sections 9.2 and 9.2.1.
- subject experiences a systemic hypersensitivity event (such as anaphylaxis) following administration of investigational product.
- subject becomes pregnant

Subjects who discontinue the study early will have end-of-study procedures as outlined in Visit 804 in the Schedule of Activities (Section 2).

## 8.3. Lost to Follow-Up

A subject will be considered lost to follow-up if he or she repeatedly fails to return for scheduled visits and is unable to be contacted by the study site. Site personnel are expected to make diligent attempts to contact subjects who fail to return for a scheduled visit or were otherwise unable to be followed up by the site.

Site personnel, or an independent third party, will attempt to collect the vital status of the subject within legal and ethical boundaries for all subjects randomized, including those who did not get

investigational product. Public sources may be searched for vital status information. If vital status is determined, this will be documented and the subject will not be considered lost to follow-up.

Lilly personnel will not be involved in any attempts to collect vital status information.

## 9. Study Assessments and Procedures

Section 2 lists the Schedule of Activities with the study procedures and their timing (including tolerance limits for timing).

Appendix 2 lists the laboratory tests that will be performed for this study.

Unless otherwise stated in the subsections below, all samples collected for specified laboratory tests will be destroyed within 60 days of receipt of confirmed test results. Certain samples may be retained for a longer period, if necessary, to comply with applicable laws, regulations, or laboratory certification standards.

### 9.1. Efficacy Assessments

#### 9.1.1. Primary Efficacy Assessments

The primary efficacy endpoint is the proportion of subjects achieving PASI 90 at Week 16 (nonresponder imputation [NRI]). PASI 90 indicates 90% improvement from baseline in PASI.

The PASI is an accepted primary efficacy measurement for this phase of development of psoriasis treatments (EMA 2004). The PASI combines assessments of the extent of body-surface involvement in 4 anatomical regions (head, trunk, arms, and legs) and the severity of desquamation (scaling), erythema, and plaque induration/infiltration (thickness) in each region, yielding an overall score from 0 for no psoriasis up to 72 for the most severe disease (Fredriksson and Pettersson 1978). The PASI has been the most frequently used endpoint and measure of psoriasis severity in clinical trials (EMA 2004; Menter et al. 2008). A clinically meaningful response is a PASI 75, which represents at least a 75% decrease (improvement) from the baseline PASI score. Higher levels of clearance (PASI 90), as well as complete resolution of psoriasis (PASI 100), have become additional endpoints because of the increasing recognition of the association of higher clearance with greater health-related quality of life (Puig 2015).

#### 9.1.2. Secondary Efficacy Assessments

Secondary efficacy endpoints are PASI 100 and PASI 75 at Week 16, sPGA at Week 16, and PASI 100, PASI 90, and PASI 75 at Weeks 52, 104, and 120.

PASI 100, 90, and 75 are percentage improvements in PASI (100%, 90%, and 75%, respectively).

The sPGA provides the physician's determination of the subject's psoriasis lesions overall at a given time point. Overall lesions are graded for induration, erythema, and scaling, and the sum of the 3 scores is divided by 3 to obtain a final sPGA score (range 0 to 5). For the analysis of responder rates, the sPGA scores are rounded to the nearest whole number, and the subject's psoriasis is assessed as clear (0), minimal (1), mild (2), moderate (3), severe (4), or very severe (5).

### **9.1.3. Additional Efficacy Assessments/Disease Activity Measures**

Percent BSA will be evaluated as the percent involvement of psoriasis on each subject's BSA on a continuous scale from 0% (no involvement) to 100% (full involvement), where 1% corresponds to the size of the subject's hand (including the palm, fingers, and thumb) (National Psoriasis Foundation 2009).

Psoriasis Scalp Severity Index (PSSI) measures the affected scalp area and the severity of clinical symptoms. If the subject has scalp psoriasis at any time during the study, the PSSI will be used for all remaining visits. The PSSI is a composite score derived from the sum of scores for erythema, induration, and desquamation multiplied by a score for the extent of scalp area involved (range 0 to 72). Higher scores indicate worse severity (Thaci et al. 2015).

Clinical whole body photographs will be collected at the times shown in the Schedule of Activities (Section 2) for patients who have given their consent to have photographs taken. Detailed instructions for obtaining clinical photographs will be provided in a study manual. Documentation of the clinical improvement will be permitted through sequential whole body photography before and after study treatment.

### **9.1.4. Health Outcomes Assessments**

The following patient-reported questionnaires will be administered according to the Schedule of Activities (Section 2) in countries where the questionnaires have been translated into the native language of the region and linguistically validated. They should be completed before administration of study drug; before the subject's clinical examination; before the subject receives any tests or results; and before the subject's health, health data, or emotions are discussed.

#### **9.1.4.1. Psoriasis Symptom Scale**

The Psoriasis Symptom Scale (PSS) is a patient-reported assessment of 8 symptoms: itch, pain, discomfort, stinging, burning, redness, scaling, and cracking. Respondents are asked to answer the questions based on their psoriasis symptoms. Numeric rating scales (NRS) are used to assess the self-reported overall severity of each of the 8 symptoms individually on an 11-point horizontal scale anchored at 0 (no) and 10 (worst imaginable). The overall severity for each individual symptom from psoriasis is indicated by selecting the number from 0 to 10 that best describes the worst level of each symptom in the past 24 hours. The instructions for completion are embedded within the PSS questionnaire for subjects to read before responding to the items. The symptom severity scores, ranging from 0 to 10, are the values of the selected numbers indicated by the subject on the instrument's horizontal scale. Each of the 8 individual items will receive a score of 0 to 10 and will be reported as item scores for itch, pain, discomfort, stinging, burning, redness, scaling, and cracking. In addition, a total score ranging from 0 (no psoriasis symptoms) to 80 (worst imaginable psoriasis symptoms) will be reported.

#### **9.1.4.2. Patient's Global Assessment of Psoriasis**

The Patient's Global Assessment of Psoriasis (PatGA) is a patient-reported, single-item scale on which subjects are asked to rank, by selecting a number on a 0-to-5 NRS, the severity of their psoriasis "today" from 0 (clear), no psoriasis, to 5 (severe).

#### **9.1.4.3. Dermatology Life Quality Index**

The Dermatology Life Quality Index (DLQI) is a patient-reported, 10-question, validated, health-related quality of life (HRQOL) questionnaire that covers 6 domains: symptoms and feelings, daily activities, leisure, work and school, personal relationships, and treatment (Basra et al. 2008; Finlay and Khan 1994). Responses to each question include "Not at all," "A little," "A lot," and "Very much," with corresponding numerical scores of 0, 1, 2, and 3 respectively. A "Not relevant" option provided for Items 3 to 10 is scored as 0. Item 7 (work or studying) comprises 2 parts, with the first part being scored as 0 for a "No" response and 3 for a "Yes" response. If one answers "No" to the first part of the question, the response options for the second part are "A lot," "A little," and "Not at all" which correspond to the numerical scores of 2, 1, and 0, respectively. If any one question is left unanswered, it is scored 0; however, if 2 or more questions are left unanswered, the DLQI is not scored. The DLQI total score is the sum of all responses to its 10 questions. The DLQI sum score has a range of 0 to 30 with lower scores indicating less impairment and higher scores indicating more dermatology-specific HRQOL impairment. A DLQI total score of 0 to 1 is considered as having no effect on a subject's HRQOL (Hongbo et al. 2005).

#### **9.1.4.4. Medical Outcomes Study 36-Item Short-Form Health Survey**

The Short-Form Health Survey (SF-36) is a 36-item, patient-reported measure designed to be a short, multipurpose assessment of health (Ware and Sherbourne 1992). Items are answered on Likert scales of varying lengths. The SF-36 acute version will be used, which has a 1-week recall period. The SF-36 has 8 domains: Physical Functioning, Role-Physical, Bodily Pain, General Health, Vitality, Social Functioning, Role-Emotional, and Mental Health. Two overall summary scores can be obtained: physical component summary (PCS) and mental component summary (MCS) scores. Individual domains are scored from 0 to 100 with higher scores indicating better HRQOL. The PCS and MCS summary scores are normalized and transformed to calculate the PCS and MCS summary scores with normative values of 50 and standard deviation of 10 (Ware et al. 2001). Minimal clinically important differences (MCID) have been defined as  $\geq 2.5$ -point increases from baseline for SF-36 PCS and MCS and  $\geq 5.0$ -point increases from baseline for individual domain scores (Strand et al. 2013).

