6.1.3. Analysis Methods

The analysis method for comparisons of each Induction Period LY3074828 dose regimen (300 mg, 100 mg, 30 mg) and placebo for categorical binary efficacy and health outcome variables will be a logistic regression analysis with treatment, geographic region (United States/Outside United States [US/OUS]), and previous biologic therapy (yes/no) using SAS PROC Logistic. Note although geographic region is not a stratification factor, due to its potential impact on outcome, unless otherwise specified, it is included in all logistic regression models. In addition, sensitivity analysis with other covariates for primary endpoint will be conducted using logistic regression (Section 6.2.1).

Logistic regression with a Firth penalized likelihood will be used (see [Appendix 1](#) for simulation study). Firth correction is equivalent to specifying Jeffrey's prior and seeking the mode of the posterior distribution. Roughly, it adds half of an observation to the data set assuming that the true values of the regression parameters are equal to 0. The likelihood function is adjusted by a fixed quantity which reduces the positive bias of small samples. The fixed quantity is a function of the information which goes to 0 as sample size increases. Firth correction can be implemented in PROC Logistic by including *firth* as an option in the model statement. The

odds ratio and the corresponding 95% CIs, as well as the treatment differences and the corresponding 95% CIs, will be reported.

In addition, linear trend tests will be performed for dose-response analysis using all 4 doses (placebo, LY3074828 30 mg, 100 mg and 300 mg). For the first test, all 4 doses will be used and the lower 3 doses will be used for the second test, and the lowest 2 doses will be used for the third test. Under the assumption of monotonic treatment response, the conclusion of trend implies that the highest dose in the test is efficacious.

1. Hypothesis 1: There is no treatment difference in PASI 90 response at Week 16 between LY 300 mg and placebo group
2. Test if there is a monotonic linear trend between the 4 doses
3. Hypothesis 2: There is no treatment difference in PASI 90 response at Week 16 between LY 100 mg and placebo group
4. Test if there is a monotonic linear trend between the 3 doses (LY 100 mg, 30 mg, and placebo)
5. Hypothesis 3: There is no treatment difference in PASI 90 response at Week 16 between LY 30 mg and placebo group.

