6.2. Adjustments for Covariates

6.2.1. Logistic Regression

The randomization is stratified by previous biologic therapy (yes/no). Unless otherwise specified, categorical efficacy variables will be analyzed using a logistic regression analysis with treatment, geographic region (US/OUS), and previous biologic therapy (yes/no) in the model. Logistic regression details are provided in Section 6.1.3.

For primary endpoint PASI 90 at Week 16, additional covariates will be added to the logistic regression as sensitivity analysis, including baseline PASI score, treatment by previous biologic use interaction, and treatment by geographic region interaction.

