 - BMI category: underweight (<18.5 kg/m²); normal (≥18.5 and <25 kg/m²); overweight (≥25 and <30 kg/m²); obese (≥30 and <40 kg/m²); extreme obese (≥40 kg/m²)
 - Alcohol use: never, current, former
 - Caffeine use: never, current, former
 - Tobacco use: never, current, former
 - Previous psoriasis therapy:
 - Previous systemic therapy: never used, non-biologic only, biologic only, biologic and non-biologic.
 - Previous non-biologic systemic therapy: never used, ever used
 - Previous biologic therapy: never used, ever used
 - Previous topical therapy: never used, topical prescription therapy, topical non-prescription therapy
 - Previous phototherapy (ultraviolet B [UVB] or PUVA): never used, ever used
- where
- Non-biologics include: methotrexate, cyclosporine, corticosteroids, acitretin, fumaric acid derivatives, apremilast, other
 - Biologics include: efalizumab, ustekinumab, infliximab, etanercept, alefacept, adalimumab, golimumab, certolizumab pegol, secukinumab, ixekizumab, other
- Duration of psoriasis (in years): Will be calculated using the date of psoriasis onset (as recorded on the Prespecified Medical History - Indication eCRF page) as follows:

$$\begin{aligned} & \textit{Duration of psoriasis (years)} \\ = & \frac{\textit{Date of informed consent} - \textit{Date of psoriasis onset}}{365.25} \end{aligned}$$

- Duration of psoriasis diagnosis (in years): Will be calculated using the date of psoriasis diagnosis (as recorded on the Prespecified Medical History - Indication eCRF page) as follows:

$$\begin{aligned} & \textit{Duration of psoriasis diagnosis (years)} \\ = & \frac{\textit{Date of informed consent} - \textit{Date of psoriasis diagnosis}}{365.25} \end{aligned}$$

- Baseline PASI score
- Baseline PASI category: $<20, \geq 20$
- Baseline PASI category: $<15, \geq 15$
- Baseline sPGA
- Baseline sPGA category: 0, 1, 2, 3, 4, 5
- Scalp psoriasis: yes, no (reported on Psoriasis Involvement eCRF form)
- Baseline PSSI score
- Baseline PSS score
- Baseline BSA (%)
- Baseline BSA category: $<20\%, \geq 20\%$
- Baseline DLQI total score
- Baseline DLQI total category: $<10, \geq 10$
- Baseline DLQI total category: $<5, \geq 5$
- Baseline DLQI total category: 0 or 1, >1
- Baseline SF-36 physical functioning score
- Baseline SF-36 role-physical score
- Baseline SF-36 role-emotional score
- Baseline SF-36 bodily pain score
- Baseline SF-36 vitality score
- Baseline SF-36 social functioning score
- Baseline SF-36 mental health score

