	Very much = 3 A lot = 2 A little = 1 Not at all = 0 Not relevant = 0	DLQI leisure domain	Sum of responses of questions #5 and #6: #5. How much has your skin affected any social or leisure activities? #6. How much has your skin make it difficult for you to do any sport?	If 1 question in a domain is missing, that domain is missing.
		DLQI work and school domain	Sum of responses of questions question #7A and #7B: #7A. Has your skin prevented you from working or studying? #7B. If No: how much has your skin been a problem at work or studying?	If the answer to question #7A is missing, this domain is missing. If #7A is No, and #7B is missing, this domain is missing.
		DLQI personal relationships domain	Sum of responses of questions #8 and #9: #8. How much has your skin created problems with your partner or any of your close friends or relatives? #9. How much has your skin caused any sexual difficulties?	If 1 question in a domain is missing, that domain is missing.
		DLQI treatment domain	Response of question #10: #10. How much of a problem has the treatment for your skin been, for example by making your home messy, or by taking up time?	If 1 question in a domain is missing, that domain is missing.
		DLQI total score	A DLQI total score is calculated by summing all 10 question responses, and has a range of 0 to 30 (less to more impairment) (Finlay and Khan 1994; Basra et al. 2008).	If 2 or more questions are missing, the total score is missing. Note: #7B could be a valid missing while #7A is not “No.” That is, #7 should be considered as 1 question.
		DLQI (0,1)	A DLQI (0,1) response is defined as a post-baseline DLQI total score of 0 or 1. A DLQI total score of 0	Missing if DLQI total score is missing

Measure	Description	Variable	Derivation / Comment	Imputation Approach if with Missing Components
			to 1 is considered as having no effect on a patient’s HRQoL (Khilji et al. 2002; Hongbo et al. 2005).	
		DLQI (0)	A DLQI (0) response is defined as a postbaseline DLQI total score of 0.	Missing if DLQI total score is missing
		DLQI total score ≥ 5	A DLQI total score ≥ 5 response is defined as a postbaseline DLQI total score ≥ 5 .	Missing if DLQI total score is missing
		DLQI total score and domain scores change from baseline	Calculated as: observed DLQI (total score or domain scores) – baseline DLQI (total score or domain scores)	Missing if baseline or observed value is missing

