SF-36	
The SF-36 is a 36-item, patient-completed measure designed to be a short, multipurpose assessment of health (The SF Community – SF-36 Health Survey Update). The summary scores range from 0 to 100, with higher scores indicating better levels of function and/or better health. Items are answered on Likert scales of varying lengths. The SF-36 comprises 8 domain scores and 2 overarching component scores. The SF-36 acute version will be used, which has a 1 week recall period.
 
Minimal Clinically Important Difference (MCID) cut-offs were determined in Strand et al. 2013.
	SF-36 Domain scores: Physical functioning, Role-physical, Role-emotional, bodily pain, vitality, social functioning, mental health, general health	
Per copyright owner, the Quality Metric Health Outcomes™ Scoring Software 4.5 will be used to derive SF-36 domain and component scores.
 
After data quality-controls, the SF-36 software will re-calibrate the item-level responses for calculation of the domain and component scores. These raw scores will be transformed into the domain scores (t-scores) using the 1-week recall period. No missing-imputation method will be used. Both, raw and domain scores without missing-data imputation will be recorded in the SDTM dataset, however only the domain scores will be used for analyses specified in this SAP.
	Missing data handling offered by SF-36 software will be used.
		SF-36 Component Scores: PCS and MCS		

Measure	Description	Variable	Derivation / Comment	Imputation Approach if with Missing Components
		SF-36 change from baseline for domain and component scores	Calculated as: observed SF-36 domain score – baseline SF-36 domain score	Missing if baseline or observed value is missing
		SF-36 Physical Component response (PCS)	PCS component score (change from baseline) ≥ 2.5	Missing if baseline or observed value is missing
		SF-36 Mental Component response (MCS)	MCS component score (change from baseline) ≥ 2.5	Missing if baseline or observed value is missing

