	DLQI total score and domain scores change from baseline	MMRM;	ITT Population	All pairwise comparisons against placebo at all postbaseline visits in Induction Period
		ANCOVA	Maintenance Period Efficacy Population	All visits in Maintenance Period
SF-36	SF-36 change from baseline for Domain Scores and Component Scores	ANCOVA	ITT Population	All pairwise comparisons against placebo at all postbaseline visits in Induction Period
		ANCOVA	Maintenance Period Efficacy Population	All visits in Maintenance Period
	SF-36 Physical Component (PCS) and Mental Component (MCS) Response	Logistic regression analysis with NRI	ITT Population	All pairwise comparisons against placebo at all postbaseline visits in Induction Period
		Summary statistics with NRI	Maintenance Period Efficacy Population	All visits in Maintenance Period
PatGA	Change from baseline	MMRM	ITT Population	All pairwise comparisons against placebo at all postbaseline visits in Induction Period
		ANCOVA	Maintenance Period Efficacy Population	All visits in Maintenance Period
PSS	PSS total score and item scores change from baseline	MMRM; mBOCF ANCOVA	ITT Population	All pairwise comparisons against placebo at all postbaseline visits in Induction Period
		ANCOVA	Maintenance Period Efficacy Population	All visits in Maintenance Period

Measure	Variable	Analysis Method (Sections 6.1.3)	Population (Section 6.1.1)	Time Point
		Summary statistics (As observed) or individual trajectory line plot if total number of subjects is too small	Rescue Period Efficacy Population	All visits in Rescue Period

Abbreviations: ANCOVA = analysis of covariance; BSA = body surface area; DLQI = Global Assessment Dermatology Life Quality Index; ITT = intent-to-treat; KM = Kaplan-Meier; mBOCF = modified baseline observation carried forward; MCS = Mental Component Score; MMRM = mixed model repeating measures; NRI = non-responder imputation; PASI = Psoriasis Area and Severity Index; PatGA = Patients Global Assessment of Psoriasis; PCS = Physical Component Score; PSS = Psoriasis Symptoms Scale; PSSI = Psoriasis Scalp Severity Index; sPGA = Static Physician Global Assessment.

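### The logistic models for SF-36 PCS and MCS response leave out the baseline score from which the response is measured, at a modest cost in power that depends on an assumed correlation

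*Protocol*

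**What the plan says.** **Model.** SAP 6.1.3 says that the method for comparing each dose with placebo on "categorical binary efficacy and health outcome variables will be a logistic regression analysis with treatment, geographic region" and previous biologic therapy, fitted with a Firth penalty. SAP 6.2.1 repeats the covariate set: "categorical efficacy variables will be analyzed using a logistic regression analysis with treatment, geographic region (US/OUS), and previous biologic therapy (yes/no) in the model". Table 6.3 (SAP 6.9) applies it, in the ITT population with nonresponder imputation (NRI), to "SF-36 Physical Component (PCS) and Mental Component (MCS) Response" and to DLQI (0,1) and DLQI (0).

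**Response definitions.** In SAP Table 6.2 the SF-36 physical response is "PCS component score (change from baseline) ≥ 2.5", with a parallel rule for MCS. The threshold comes from Protocol 9.1.4.4, where "Minimal clinically important differences (MCID) have been defined as" rises of at least that size in PCS and MCS. For the DLQI, the same table says "A DLQI (0,1) response is defined as a post-baseline DLQI total score of 0 or 1". Protocol 9.1.4.3 gives the reason: "A DLQI total score of 0 to 1 is considered as having no effect on" quality of life.

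**Where baseline is used.** The continuous SF-36 analysis is an ANCOVA and the continuous DLQI analysis in induction is an MMRM. Both include the baseline value (SAP 6.1.3, 6.2.2, 6.2.3). The only baseline severity score added to a main-endpoint logistic model is PASI, for PASI 90 at Week 16, as a sensitivity analysis (SAP 6.2.1).

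**Status of the endpoints.** The Protocol Synopsis lists mean change, not responder rate, as the secondary SF-36 and DLQI endpoint.

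**The concern.** An SF-36 response is a thresholded change score, so baseline is one of its two ingredients. A subject who happens to score low at Week 0 tends to rise, and one who scores high tends to fall. The baseline score is therefore a natural predictor of response, and it is already collected. In induction the Schedule of Activities places the SF-36 only at Week 0 and Week 16, so there are no intermediate visits to draw on.

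The SAP treats the same scale in two ways, with baseline adjustment when it is continuous and without it when it is dichotomised, and gives no reason. At stake is some power in each comparison of a dose with placebo at 50 subjects per arm. The DLQI responder models share the covariate set, but there baseline matters only as far as it predicts the final score.

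**Working it through.** **1. The plan's own figure.** SAP 5.2 assumes 50 per arm, PASI 90 rates of 60% and 3%, and a two-sided Fisher's exact test at 0.05, and states power over 99%. Exact enumeration gives 0.9999999, so the figure reproduces. It concerns a different endpoint. Neither document gives a power, SD, correlation or expected rate for SF-36 or DLQI response, so what follows is conditional on assumed values.

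**2. How baseline enters the SF-36 response.** Give baseline and Week 16 scores unit SD and correlation ρ. Then Var(change) = 2(1−ρ) and Cov(change, baseline) = ρ−1, so Corr(change, baseline) = −√((1−ρ)/2). At ρ = 0.5 this is −0.5.

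**3. Approximate loss.** Take the share of efficiency lost as the R² of the binary response on baseline under bivariate normality:

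loss = c² × φ(z_p)² / [p(1−p)]

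Here p is the response rate, z_p its normal quantile and φ the normal density. For the SF-36 change response c² = (1−ρ)/2. For a response defined on the final score alone, such as DLQI (0,1), c² = ρ².

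Example, SF-36, ρ = 0.5:
- p = 0.5: 0.25 × 0.1592/0.25 = 0.159.
- p = 0.3 or 0.7: 0.25 × 0.1209/0.21 = 0.144.

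**4. Simulation, SF-36 response.** 1,500 trials per scenario, 50 per arm. Firth logistic regression with treatment and two binary covariates was fitted with and without baseline. The response threshold is 0.25 SD (2.5 points on an SD of 10), and the effect is 0.6 SD of the change score. Loss = 1 − (mean z without baseline / mean z with baseline)². Power is the share of trials with |z| > 1.96.

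| ρ | Rates, placebo vs active | Formula loss, p 0.3 to 0.7 | Simulated loss | Power without baseline | Power with baseline |
|---|---|---|---|---|---|
| 0.3 | 42% vs 65% | 20.1% to 22.3% | 18% | 61.5% | 72.2% |
| 0.5 | 40% vs 63% | 14.4% to 15.9% | 13% | 60.5% | 67.7% |
| 0.7 | 37% vs 61% | 8.6% to 9.5% | 6% | 61.7% | 66.2% |
| 0.9 | 29% vs 52% | 2.9% to 3.2% | 1% | 62.2% | 63.3% |

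At ρ = 0.5 the unadjusted test with 50 per arm does the work of 50 × 0.87 = 43.5 per arm with baseline in the model.

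The gain does not come from a smaller standard error. At ρ = 0.5 the SE of the log odds ratio rises from 0.425 to 0.475, while the estimate rises from 0.95 to 1.13, because the odds ratio becomes conditional on baseline. The loss is therefore a statement about the test, not about the precision of the log odds ratio.

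**5. DLQI (0,1).** Same simulation, at 16% vs 50% response:

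| ρ | Formula loss, p 5% to 60% | Simulated loss | Power without baseline | Power with baseline |
|---|---|---|---|---|
| 0 | 0% | −2% | 94.7% | 94.7% |
| 0.2 | 0.9% to 2.5% | 0% | 94.8% | 94.9% |
| 0.3 | 2.0% to 5.7% | 2% | 95.1% | 95.7% |
| 0.5 | 5.6% to 15.9% | 7% | 95.5% | 97.2% |

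At 5% vs 60% and ρ = 0.3 the simulated loss is 0.4%. The −2% at ρ = 0 means that an uninformative covariate slightly weakens the test. DLQI (0) was not simulated separately; the same formula applies.

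**6. Cross-check with a different test.** A second simulation used the penalised likelihood-ratio test, 2,000 runs per scenario.
- PCS response (SD 9, ρ 0.4 to 0.6, effects of 4 to 5 points, about 43% vs 61% to 65%): relative efficiency 1.11 to 1.21. The losses are 1 − 1/1.11 = 9.9% to 1 − 1/1.21 = 17.4%, with power gains of 1 to 6 points.
- DLQI (0,1) at 10% vs 30%, with baseline log-odds of 0.8 to 1.2 per SD: relative efficiency 1.06 to 1.11, so losses of 5.7% to 9.9%. Those log-odds correspond to a latent correlation of about 0.40 to 0.55, so this is the strong-baseline end of step 5.

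**The case against.** The case for leaving the SAP alone is reasonable. These responder analyses are neither primary nor secondary endpoints in the protocol. The mean-change analyses of the same scales are baseline-adjusted, and no stated decision rests on responder power. Randomisation keeps the unadjusted test valid. The shorter model uses one covariate set for the binary endpoints and needs no rule for missing baselines. All of this stands, and it makes the point minor. It does not remove the power gain for SF-36 response at most plausible correlations.

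Four stronger readings are tempting, and the documents do not support them.

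- **That the DLQI (0,1) definition also depends on baseline.** It refers only to the post-baseline total. Eligibility sets no DLQI minimum and the SAP tabulates "Baseline DLQI total category: 0 or 1, >1", so a subject could start at 0 or 1 and count as a responder without change. But entry requires PASI of at least 12, at least 10% body surface area and sPGA of at least 3, and nothing shows that such subjects would be common.
- **That up to 21% of the sample is given away.** A relative efficiency of 1.21 is the extra sample that the unadjusted test would need; the share lost is about 17%. No single range fits both scales, and the lower end for the DLQI is nil.
- **That the omission has no benefit.** It has the simplicities named above.
- **That subjects near normal cannot gain 2.5 points.** The value of 50 in Protocol 9.1.4.4 is a population norm, not a ceiling. The argument rests on regression to the mean.

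**Conclusion.** The point holds for SF-36 PCS and MCS response as a small inefficiency, not an error. With 50 per arm the planned test loses about 18%, 13%, 6% and 1% of its efficiency at assumed correlations of 0.3, 0.5, 0.7 and 0.9. These figures assume roughly normal scores with equal variance at both visits and response rates in the middle range. The trial documents supply none of these inputs, so the range is a set of scenarios and not an estimate.

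For DLQI (0,1) and DLQI (0), baseline adjustment is optional. The expected gain is about 0% to 2% at correlations up to 0.3 and about 7% at 0.5. The primary endpoint and the protocol's secondary SF-36 and DLQI endpoints are unaffected.

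**What to change.** In SAP 6.2.1 and the SF-36 response rows of Table 6.3, state that the PCS response model also includes the baseline PCS score, and the MCS response model the baseline MCS score, as a continuous covariate. Optionally add the baseline DLQI total to the DLQI (0,1) and DLQI (0) models.

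State a rule for missing baselines: set them to the overall mean. Under Table 6.2 and NRI, a subject without a baseline SF-36 score is kept as a nonresponder. A model with a missing covariate would drop that subject, and the rule leaves the ITT set unchanged.

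The cost is a sentence or two in the SAP and one covariate in the code, with no new data. There are two downsides: the odds ratio becomes conditional on baseline as well, and the covariate set then differs across binary endpoints. If Week 16 results have already been unblinded, report the adjusted model as a labelled sensitivity analysis.
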